## 3.3 Inclusion of Women and Minorities

Recruitment to this study is expected to be similar to national data on cancer survivors population and the demographics of the WFBCCC. We expect  $>50\%$  of enrolled participants to be women survivors. We will not enroll children ( $\leq 18$  years) as the research pertains to older adult survivors. Based on our cancer center data, we expect approximately 3% of participants to be Hispanic/Latino (n=2). The breakdown of racial categories is expected to be as follows: 14% Black or African American (n=9), 84% White (n=54) and 2% more than 1 race (n=1). Should we

not meet or exceed these estimates, the PI will engage the Office of Cancer Health Equity to discuss strategies to enhance recruitment in these target populations. Our cancer center has policies in place to enhance recruitment of minority participants and will provide translation of the protocol and informed consent into Spanish.

## **4.0 Recruitment and Registration Procedures**

### **4.1 Recruitment**

Participants will be recruited from the community via advertisement in the Center for Health Aging and Alzheimer's Prevention Newsletter, newspaper advertisement, postcard mailing, and through sharing information with interested community organizations. Subjects will also be recruited from the Wake Forest Baptist Cancer Center (WFBCCC) using flyer advertisement including but not limited to Survivorship Clinics, mailings to participants, and messages via MyWakeHealth, listing the trial in the WFBCCC clinical trial website used by providers and monitoring trial recruitment through the Cancer Control and Survivorship Disease Oriented Team. Interested participants will contact the MGE Team Clinical Coordinators who will conduct prescreening by phone and coordinate in person visits for eligible patients in the Clinical Research Unit, or at the High Point, Wilkes, or Statesville clinic sites.

### **4.2 Screening**

Study coordinators will pre-screen appropriate patients to assess eligibility via IRB-approved HIPAA waiver. Patients who are eligible will be contacted by phone or encountered at a clinic visit. Study coordinators will explain the study to potential participants to determine their interest and willingness. If a patient is likely eligible, but there is not adequate information available to confirm eligibility, the patient will be re-contacted for further assessment. If the patient has documentation of the necessary laboratory studies within the specified window that does not appear in the medical record, the study coordinator will obtain and review these documents. If the patient needs additional studies in order to assess eligibility, the study coordinator will arrange to obtain the necessary studies. Signed consent for eligibility screening will be obtained prior to performing the additional studies. If the patient meets eligibility criteria, the study coordinator will arrange for the baseline study visit, which will include informed consent, registration, randomization, and day 1 study activities.

### **4.3 Registration**

All participants entered on any WFBCCC trial, whether treatment, companion, or cancer control trial, **must** be linked to the study in EPIC within 24 hours of Informed Consent. Participant **must** be registered prior to the initiation of treatment.

1. Complete the Eligibility Checklist (Appendix A)
2. Complete the Protocol Registration Form (Appendix B)
3. Register the participant in OnCORE – this will alert the cancer center registrar, who will then review the signed informed consent and confirm the eligibility.

Contact Information:

Protocol Registrar [contact]

Protocol Registrar [contact]

Protocol Registrar E-MAIL ([[contact]](mailto:[contact]))

4. Participant **will not** be registered without all required supporting documents.

Note: For any screening activities performed at an outside institution, the source documentation must be provided

To complete the registration process, the study team will:

1. Register the participant on the study
2. Assign a participant study number
3. Randomize the participant

#### **4.4 Blinding**

This is a double-blind study. Only the investigational pharmacists and the statisticians will be unblinded. The blind will be maintained until the study is complete.

### **5.0 Study Outcomes and Study Measures**

#### **5.1 Primary Outcome**

5.1.1 Patient Reported Outcomes Measurement System (PROMIS) Fatigue 7a will be used to assess fatigue. Fatigue is divided into the experience of fatigue (frequency, duration, and intensity) and the impact of fatigue (upon physical, mental, and social activities). Item responses are rated on a five-point scale ranging from “never” to “always” and are summed for a total score and transformed to a T-score metric, which has a mean of 50 and a standard deviation of 10. Higher scores indicate more fatigue. The PROMIS Fatigue Short-Form 7a has shown robust reliability and validity across multiple samples.

#### **5.2 Secondary Outcomes**

5.2.1 The **Pepper Assessment Tool for Disability (PAT-D)** will be used to assess self-reported physical function. The (PAT-D) is a 19-item survey designed by Rejeski et al. to assess domains of physical function in older adults which contains subscales on mobility, instrumental (IADLs), and basic activities of daily living (ADLs).

5.2.2 The **Short Form Minnesota Leisure Time Activity Questionnaire (MLTA)** will assess self-reported physical activity.

5.2.3 The **Short Physical Performance Battery (SPPB)** will be used to objectively assess lower extremity physical function. This validated measure comprises a short walk, repeated chair stands, and balance test. Lower scores on the SPPB have been associated with increased risk of disability, hospitalization and worse survival among older adults with and without cancer.

5.2.4 The **6-minute walk** will be measured to assess physical fitness. The 6-minute walk is easy to administer in a clinical setting, accurately assesses submaximal exercise

capacity, is an independent predictor of mortality and is correlated with peak V02 testing.

- 5.2.5 The **Longitudinal Aging Study Amsterdam (LASA) Sedentary Behavior Questionnaire** will be used measure sedentary behavior.
- 5.2.6 The **PROMIS Global Health Short Form (SF)** will assess global QOL This is a 10-item instrument representing multiple domains inclusive of physical, mental and social health in adults.
- 5.2.7 **Adherence** will be measured by pill count at study completion.
- 5.2.8 The following measures of interest will be collected to allow characterization of frailty (Fried Frailty Phenotype), **Center for Epidemiologic Studies Depression Scale (CES-D)**, **MLTA questionnaire**, **Grip strength**, **self-reported weight loss**.

### **5.3. Exploratory outcomes**

- 5.3.1 Peripheral blood will be collected at the baseline and week 12 study visit, and will be processed to obtain serum for the measurement of cytokines including interleukin 6 (IL-6), tumor necrosis factor-alpha (TNF- $\alpha$ ), C reactive protein (CRP) and HGF and polymorphonuclear neutrophils (PMNs) to measure mitochondrial function. Cytokines and 8-OHdG will be measured using human ELISA kits (Abcam) and mitochondrial function will be assessed using a Seahorse XF Cell Mito Stress Test (Agilent).
- 5.3.2 Urine will be collected at baseline and 12 weeks to measure the oxidative stress marker 8-OHdG and urolithin A glucuronidate (UAG), a marker for the ingestion/metabolism of MGE. UAG, which is generated from the ingestion of MGE polyphenolic ellagitannins, will be measured using an LCMS-8050 triple quadrupole mass spectrometer in the Wake Forest School of Medicine Proteomics and Metabolomics Shared Resource.
- 5.3.4 Fecal specimens will be collected at baseline and at ~12 weeks using an at-home fecal sampling kit. Samples will be collected by the patient prior to the initiation of intervention and again near the completion of intervention. Patients will be asked to mail samples in a pre-paid package to the laboratory. DNA will be isolated from fecal samples using the Qiagen DNeasy PowerSoil Pro kit protocol. Metagenomic sequencing will be performed by CosmosID Inc. (Rockville, MD). In brief, DNA libraries will be prepared using the Illumina Nextera XT library preparation kit, with a modified protocol. Library quantity will be assessed with Qubit (ThermoFisher). Libraries will be sequenced on an Illumina HiSeq platform 2x150bp. Fecal samples will be read at 12M read-depth. Unassembled sequencing reads will be directly analyzed by CosmosID bioinformatics platform for multikingdom microbiome analysis and quantification of organism's relative abundance. Fecal microbiomes will be assessed by metagenomic sequencing and bioinformatics. A list of all the microbiologic species will be recorded, along with their relative abundance recorded as a % relative abundance of the total microbiome.
- 5.3.5 Digit Symbol Substitution Test (DSST) is a measure of attention and perceptual speed, amenable to change with exercise or fatigue in which participants are given a

series of numbered symbols and then asked to draw the appropriate symbols below a list of random numbers. The score is the number of correctly made matches in 2 minutes (120 seconds).

#### **5.4. Adverse events (AEs)**

AEs will be assessed by the study team at each visit (by phone or in person). AEs of interest are flatulence, diarrhea, nausea, dyspepsia, constipation, abdominal pain (see Appendix P). Other possibly/probably attributable adverse events will be recorded in addition to any serious adverse event.

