### **6.8 Duration of Follow Up**

Patients will be followed for toxicity/adverse events for 30 days after the last dose of the study drug.

Patients will be instructed to inform the study staff of any medical concerns that arise during the first 30 days after stopping the study drug for any reason. The study team will assess for toxicity/adverse events and determine attribution. Of note, a 24-hour washout period was adequate in the Phase 1 protocol with the same drug (CCCFU #01815, manuscript under review). Participants will also be called by the study team for the End of Treatment Assessment tele-visit 30 days after last study dose to review toxicity and assess resolution/stabilization of reported AEs.

Patients removed from the study intervention for unacceptable adverse events will be followed until resolution or stabilization of the adverse event. All participants who discontinue taking the study drug (see section 6.5) will be asked to continue study visits per protocol. If they are unable or unwilling to come to the CRU or participating site as planned, study staff will attempt to collect

fatigue and other QOL data by phone in lieu of study visits as long as consent is not withdrawn. All participants will be followed for the study outcomes until the end of the study.

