## 8.0 Adverse Events List and Reporting Requirements

### 8.1 Adverse Event List for MGE

Expected: Based on previous studies, minimal AEs are expected, which may include flatulence, diarrhea, nausea, dyspepsia, constipation, and abdominal pain.

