### 8.2 Adverse Event Characteristics

- **CTCAE term (AE description) and grade:** The descriptions and grading scales found in the revised NCI Common Terminology Criteria for Adverse Events (CTCAE) version 5.0 will be utilized for AE reporting. All appropriate treatment areas should have access to a copy of the CTCAE version 5.0. A copy of the CTCAE version 5.0 can be downloaded from the CTEP web site (<http://ctep.cancer.gov>).
- **‘Expectedness’:** AEs can be ‘Unexpected’ or ‘Expected’ (see Section 7.1 above) for expedited reporting purposes only.
- **Attribution of the AE:**
  - Definite – The AE **is clearly related** to the study intervention.
  - Probable – The AE **is likely related** to the study intervention.
  - Possible – The AE **may be related** to the study intervention.
  - Unlikely – The AE **is doubtfully related** to the study intervention.
  - Unrelated – The AE **is clearly NOT related** to the study intervention.

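### Section 5.4 uses attribution as a condition for recording, so non-serious symptoms outside the six GI terms that staff judge unlikely or unrelated go unrecorded in both arms

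*Combined protocol and SAP*

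**What the plan says.** Section 5.4 sets both the ascertainment and the recording rule. Ascertainment is broad: "AEs will be assessed by the study team at each visit (by phone or in person"). Recording is narrower and has three routes:

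- The named events: "AEs of interest are flatulence, diarrhea, nausea, dyspepsia, constipation, abdominal pain". No attribution condition is attached.
- Events outside that list, and serious events: "Other possibly/probably attributable adverse events will be recorded in addition to any serious adverse event". This gives one route that depends on attribution and one (seriousness) that does not.

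Section 8.2, under "Attribution of the AE", defines five levels, the last being "Unrelated – The AE is clearly NOT related to the study intervention". The Possible level asks only that the event may be related.

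On who judges, Section 6.8 (follow-up after the last dose) says: "The study team will assess for toxicity/adverse events and determine attribution". Section 4.4 says: "Only the investigational pharmacists and the statisticians will be unblinded".

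Section 8.1 introduces the expected list with "Based on previous studies, minimal AEs are expected". Section 12 contains no analysis or tabulation of adverse events.

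**The concern.** In a randomised, double-blind, placebo-controlled trial, comparing the arms is the sound way to find out whether an event is caused by the product. That comparison needs events to be recorded before anyone decides on cause. Section 5.4 reverses the order for non-serious events outside the GI list: the judgement on cause decides whether the event becomes data.

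The events at risk are those nobody has reason to link to MGE yet. The prior human data described in Section 1.3 are limited: a completed Phase 1 study of 23 patients with advanced solid tumours, median time on therapy 8 weeks, and a prostate cancer trial still recruiting. In survivors aged 65 and over, a non-serious symptom such as dizziness, rash or poor sleep can plausibly be put down to age or comorbidity. If it is, it leaves no trace in either arm, and it cannot be reliably recovered afterwards. The pilot's safety summary would then show fewer events than participants reported, and a later trial would be planned on that summary.

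**Working it through.** **1. Which events have a route into the data**

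| Event | Route | Depends on attribution? |
|---|---|---|
| Six GI terms | 5.4, events of interest | No |
| Any serious event | 5.4 | No |
| Unexpected grade 4, unplanned hospitalization > 24 h, death | 8.3, STRC reporting | No |
| Blood count and chemistry changes | 6.1, 6.6.2, follow-up labs | No |
| Vital sign changes | 6.1, 6.6.1 | No |
| Other non-serious symptom, at least possibly related | 5.4 | Yes, and recorded |
| Other non-serious symptom, unlikely or unrelated | None found | Yes, and not recorded |

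The gap is the last row. Nothing else in the visible documents says that all adverse events are recorded.

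**2. Fit with Section 8.2**

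The Unlikely and Unrelated levels can still be used for serious events and for the six GI terms. For every other non-serious event, Section 5.4 leaves them with nothing to classify.

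**3. Size of the effect**

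The documents give no adverse event rate, no attribution share and no safety power figure, so there is no plan figure for this point to reproduce. The only plan input is the group size in Section 12.4: 30 per group with 5% dropout, 30 / 0.95 = 31.6, rounded up to 32. This agrees with the stated 32.

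Assumptions, not from the documents: true incidence of one unlisted non-serious symptom is p0 on placebo and p1 on MGE. Blinded staff rate a share q of these events as attributable, equally in both arms.

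- Expected recorded count per arm = 32 × p × q
- Recorded risk difference = q × (p1 − p0)
- Recorded risk ratio = (q × p1) / (q × p0) = p1 / p0, so q cancels

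Power is for Fisher's exact test at two-sided 0.10, counting only results in the direction of an MGE excess.

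Case A, p0 = 10%, p1 = 25%:

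| q | Recorded, placebo v MGE | Difference | Ratio | Fisher power |
|---|---|---|---|---|
| 1 | 3.2 v 8.0 | 15 points | 2.5 | 34% |
| 0.5 | 1.6 v 4.0 | 7.5 points | 2.5 | about 12% |
| 0.25 | 0.8 v 2.0 | 3.75 points | 2.5 | 2% |

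Case B, p0 = 10%, p1 = 30%:

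| q | Recorded, placebo v MGE | Difference | Ratio | Fisher power |
|---|---|---|---|---|
| 1 | 3.2 v 9.6 | 20 points | 3 | 53% |
| 0.75 | 2.4 v 7.2 | 15 points | 3 | 37% |
| 0.5 | 1.6 v 4.8 | 10 points | 3 | 20% |
| 0.25 | 0.8 v 2.4 | 5 points | 3 | 4% |

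The absolute difference falls in proportion to q and the expected ratio does not move. In Case A, the chance of seeing at least three more events on MGE than on placebo falls from 78% (q = 1) to 47% (q = 0.5) and 20% (q = 0.25).

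**The case against.** The strongest counter-case has five parts.

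- **Blinding.** Those judging attribution do not know the arm, so unless they guess it, the filter acts equally on both arms and the expected risk ratio is preserved. This stands. It rules out a claim of bias towards MGE, but it does not bring back the lost events or the absolute difference.
- **A low threshold.** An event that may be related counts as Possible, so q could be close to 1. This also stands as a possibility. Nothing in the documents fixes q, and it remains a judgement made event by event.
- **Other capture.** Serious events, STRC-reportable events, laboratory tests and vital signs are collected without regard to cause, so a haematological, hepatic, renal or blood pressure effect could still be compared. This stands, and it limits the gap to non-serious clinical symptoms.
- **Forms not in the file.** Section 5.4 points to Appendix P, staff forms are held in the eIRB application, and the content of the REDCap adverse events log listed in Section 11.0 is not given. These may collect more than Section 5.4 says. If so, the remedy is to bring 5.4 into line with them; their absence here is no fault in the plan.
- **Purpose.** Safety is not among the objectives in Section 2, and targeted collection in a 64-person pilot is partly a design choice. True, but the broader record costs little at contacts where adverse events are already asked about.

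A reader might go further and infer that an unexpected effect of MGE could not be seen at all, or that the filter destroys a signal that full recording would have shown. The documents support neither. Events rated at least possible are recorded in both arms, and the difference vanishes only at q = 0. Full recording would not settle the matter either: 3 v 8 cases of 32 gives a two-sided Fisher p of 0.18, and power in Case A is only 34% with every event recorded.

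A reader might also infer that expecting few events biases staff towards calling events unrelated. No passage says so, and Section 8.2 confines expectedness to expedited reporting.

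**Conclusion.** The point holds as a limited defect in a stated rule. As written, Section 5.4 leaves non-serious, non-GI symptoms judged unlikely or unrelated out of the data in both arms, and it sits awkwardly with the five-level scale in Section 8.2. The consequences are an understated total AE incidence and a between-arm difference multiplied by q. At an assumed q of 0.25 to 0.5, a true 15-point difference would appear as about 4 to 7.5 points. There is no built-in advantage to either arm.

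The reading of the text rests on Section 5.4 meaning what it says, since the operative forms cannot be checked. The size rests entirely on assumed incidences, an assumed q and equal attribution across arms. No conclusion about the primary outcome or the sample size is affected.

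**What to change.** 1. Reword Section 5.4 so that every new or worsened adverse event reported at a scheduled contact is recorded, with CTCAE grade and the Section 8.2 attribution entered as data fields and not used as a condition for entry. The six GI terms can stay as events of specific enquiry.
2. Check Appendix P and the REDCap log against the new wording and align them if needed.
3. Add to Section 12 a descriptive tabulation by arm, once for all adverse events and once for those judged attributable. None is planned now.

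Cost: more log entries for 64 participants. Section 6.1 already schedules adverse event assessment at baseline, weeks 2, 4, 8 and 12, and the end-of-treatment call, so no visit, procedure or participant is added. The rules in Section 7.2 for holding or stopping study drug are not touched.

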## 6.0 Intervention Plan

### 6.1 Study-Related Activities

Measures / Timepoints	Pre-Study a	Baseline	Wk 2	Wk 4	Wk 8	Wk 12	End of Trtmt Visit h
Informed consent	X						
Medical and oncologic history	X						
Concomitant medications assessed by self-report j	X	X	X	X	X	X g, j	
Karnofsky Self-Reported Performance Rating Scale		X					
Vital signs		X					X j
Adverse event assessment		X	X	X	X	X g, j	X
Drug dispensing b		X					
Pill count							X g, j
Telephone follow-up c			X	X	X		
Cognitive/Physical function & fitness (DSST, SPPB, 6-min walk, grip strength)		X					X j
CBC with differential d	X						X j
Serum chemistries d	X						X j
(Partially fasting) labs for phenolic levels (blood and urine) e		X					X j
(Partially fasting) labs for correlative studies e (blood and urine)		X					X j
Stool sample collection f		X					X j
PROMIS Fatigue survey		X	X	X	X	X g, j	X
Other patient reported outcomes (PAT-D, LASA, PROMIS Global Health, CES-D, MLTA, Self-reported weight loss) j		X					X g, j
Participant Feedback							X i, j

a Labs to assess eligibility must be completed within 30 days prior to the first dose of MGE/placebo.

b Study drug (MGE or placebo) will be dispensed as a 90-day supply at the baseline visit.

c Adherence and symptom review will be assessed at each study visit. In addition, participants will be contacted by phone as follows,  $\pm 3$  days: Wk2, Wk4, Wk8.

d Safety laboratory assessments must be done within 30 days of first dose of MGE/placebo and then on the study visits indicated. These labs include:

Complete blood count (CBC) with differential: WBC count with differential, platelet count, hemoglobin/hematocrit.

Serum chemistries (complete metabolic panel, CMP): sodium, potassium, chloride, bicarbonate, blood urea nitrogen, creatinine with creatinine clearance, glucose, aspartate aminotransferase (AST), alanine aminotransferase (ALT), total bilirubin, alkaline phosphatase.

e Phenolic levels and other research labs will be obtained at baseline, and 12 weeks ( $\pm 14$  days). Patients are asked to avoid coffee, tea, fruit juice, fruit, chocolate or wine after midnight prior to blood draw.

f Two kits will be provided to participant at baseline, with detailed instructions for how and when to collect stool at home.

g If a participant is unable to attend an in person study visit for any reason including COVID-19 related reasons, all patient reported measures will be collected in a phone study visit.

- h End of Treatment Visit will be conducted by phone 30 days (+14 day window) after last dose of study medication. For those who end treatment prior to week 12, the End of Treatment Visit can be combined with another existing study visit, if that visit occurs 30-44 days after the last dose of study medication.
- i Participant feedback will be collected in person at Wk12 visit (+30 day window), or by phone at Wk16.
- j Follow-up study visits will occur at 12 weeks and will have a  $\pm$ 14 day allowance window which includes not just the visit itself, but any of the activities at that visit. For example, if labs cannot be collected at the actual study visit, the  $\pm$ 14-day window permits a second attempt at lab collection; all activities, however, must be completed in the  $\pm$ 14-day window from the expected visit date.

